3.8 Efficacy Assessment

Primary Outcome Measures: Post-treatment (immediate and 2-week follow-up) upper extremity Fugl-Meyer Assessment score, Brunnstrom staging, and Modified Ashworth Scale grading; neuroimaging data (analysis of ALFF, fALFF, ReHo, FC, and FA indices using functional MRI and diffusion tensor imaging); EEG measurements of resting-state and task-state spectral power and functional connectivity.

Secondary Outcome Measures: Blood biochemistry, complete blood count, C-reactive protein (CRP), interleukin-6 (IL-6), S100 β protein, and brain-derived neurotrophic factor (BDNF).

4. Risks and Benefits

4.1 Potential Risks and Mitigation Measures: Abnormal reactions to ultrasound stimulation and potential induction of seizures. Adverse symptoms such as dizziness and headache will be promptly managed. Short-term administration of analgesic agents and antiepileptic medications will be employed as indicated.

4.2 Potential Benefits and Compensation for Participants:

Direct Benefits: Promotion of hemiplegic upper limb functional recovery and enhancement of activities of daily living capacity.

Societal Benefits: It is anticipated that information obtained from this study may benefit the participant or future patients with similar conditions.

5. Adverse Event Monitoring

5.1 Adverse Events (AEs): An adverse event is defined as any unfavorable medical occurrence, unanticipated illness or injury, or unexpected clinical sign (including abnormal laboratory findings) in a participant or other individual, regardless of whether it is considered related to the study intervention or treatment strategy under investigation.

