Treatment Protocol	Neuromodulation Group: Multimodal neuromodulation targeting specific neural regions in addition to conventional therapy. Control Group: Sham stimulation in addition to conventional therapy.
Efficacy Assessment	Primary Outcome Measures: Fugl-Meyer Assessment score; neuroimaging data (cranial CT/MRI); EEG measurements of resting-state and task-state spectral power and functional connectivity; laboratory parameters (complete blood count, CRP, IL-6, S100 β , BDNF). Secondary Outcome Measures: Brunnstrom staging, Modified Ashworth Scale grading, muscle strength, and patient comfort assessment. Safety Assessment Indicators: Complete blood count, blood biochemistry, coagulation function.
Statistical Methods	Key outcome measures will be compared between the neuromodulation group and the control group before and after intervention using independent samples t-tests (two groups) or analysis of variance (multiple groups) to detect statistically significant intergroup differences. Non-parametric tests will be applied to data not conforming to a normal distribution.
Study Duration	March 2026 – March 2028

1. Background and Rationale

According to the World Health Organization (WHO), stroke is the second leading cause of death globally [1]. Approximately 15 million individuals worldwide experience a stroke annually, ranking second only to heart disease, and stroke remains one of the most prevalent causes of long-term disability. Ischemic stroke (IS) constitutes the most common subtype, accounting for approximately 85% of all stroke cases [2]. Among all stroke survivors, over 60% experience varying degrees of functional impairment within three months following the event. The American Stroke Association (ASA) has reported [3] that approximately one-third of stroke patients develop severe speech impairment post-stroke, while one in two patients sustains some degree of hand function loss. Stroke patients frequently contend with chronic functional deficits, including motor difficulties, speech impairment, and cognitive dysfunction, all of which profoundly compromise quality of life. These patients typically require prolonged rehabilitation and nursing care, imposing substantial financial burden on families and exerting considerable pressure on healthcare systems.

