In this context, transcranial focused ultrasound (tFUS), as an emerging noninvasive neuromodulation technology, has exhibited distinctive technical advantages [7], presenting novel possibilities for breakthroughs in ischemic stroke treatment [8]. Compared with conventional neuromodulation modalities, tFUS possesses exceptionally high spatial

resolution, enabling precise focusing on lesion sites within deep brain regions and targeted modulation of specific neural networks, thereby effectively circumventing interference with surrounding normal brain tissue. Simultaneously, tFUS requires no craniotomy, is entirely noninvasive, significantly reduces the risk of complications, improves patient treatment compliance, and offers adjustable stimulation depth applicable to ischemic stroke patients with varying lesion depths. Additionally, tFUS can modulate blood-brain barrier permeability [9], facilitating the delivery of neurorepair-related pharmacological agents to lesion sites and achieving synergistic effects between neuromodulation and pharmacotherapy.

Therefore, conducting research on tFUS neuromodulation in ischemic stroke patients is of considerable importance. Such research not only addresses the technological shortcomings of existing neuromodulation therapies by providing safer, more precise, and more effective treatment strategies for ischemic stroke patients, but also further elucidates the intrinsic mechanisms of neural repair following ischemic stroke, thereby advancing both theoretical innovation and clinical translation in the field of stroke neuromodulation [10].

2. Study Objectives

2.1 Primary Objective: This study aims to evaluate how tFUS technology promotes the remodeling of damaged neural networks and functional recovery by activating or inhibiting neural activity in specific brain regions, integrating EEG and MRI signal analyses. The primary goals are to improve motor ability and cognitive function, reduce long-term disability, and enhance quality of life. Additionally, this study seeks to optimize stimulation parameters to achieve maximal rehabilitative outcomes and to elucidate the potential mechanisms underlying neuroprotection and functional reconstruction following stroke.

2.2 Secondary Objective: To explore novel therapeutic protocols for upper limb rehabilitation following stroke.

3. Study Overview

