Five neuromodulation sessions are administered in total. Sessions 2 and 5 involve simultaneous EEG-coupled ultrasound neuromodulation, while Sessions 1, 3, and 4 consist of ultrasound neuromodulation alone. During EEG-coupled sessions, EEG signals are acquired before, during, and after ultrasound stimulation; during standalone sessions, only ultrasound stimulation is delivered without EEG acquisition. Stimulation parameters are maintained at consistent control levels across participants. Based on each individual's

cranial acoustic parameters, the pre-attenuation stimulation intensity is back-calculated to ensure uniform in situ intensity at the target. The spatial-peak temporal-average intensity at the target is maintained below the diagnostic ultrasound safety threshold (720 mW/cm²). The ultrasound stimulation duration is 12 minutes using a 20% duty cycle pulse sequence.

The post-test cranial MRI protocol is identical to the pre-test and is performed within two days of completion of all neuromodulation sessions.

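### The synopsis and Section 3.8 give partly contradictory primary outcome lists, neither names a deciding outcome or time, and several aims in the primary objective are not measured

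*Protocol*

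**What the plan says.** The synopsis (Efficacy Assessment) lists "Primary Outcome Measures: Fugl-Meyer Assessment score; neuroimaging data (cranial CT/MRI); EEG measurements of resting-state and task-state spectral power and functional connectivity", and continues with "laboratory parameters (complete blood count, CRP, IL-6", S100β and BDNF, all as primary. It then gives "Secondary Outcome Measures: Brunnstrom staging, Modified Ashworth Scale grading, muscle strength, and patient comfort assessment".

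Section 3.8 lists "Primary Outcome Measures: Post-treatment (immediate and 2-week follow-up) upper extremity Fugl-Meyer Assessment score, Brunnstrom staging, and Modified Ashworth Scale grading", followed by five MRI and diffusion indices and by EEG power and connectivity at rest and on task. The blood markers move down: "Secondary Outcome Measures: Blood biochemistry, complete blood count, C-reactive protein (CRP), interleukin-6 (IL-6", S100β and BDNF. Muscle strength and comfort do not appear there.

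The primary objective, worded the same in the synopsis and in Section 2.1, states: "The primary goals are to improve motor ability and cognitive function, reduce long-term disability, and enhance quality of life". It adds the optimisation of stimulation parameters. Section 3.6 says of the intervention: "Stimulation parameters are maintained at consistent control levels across participants".

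**The concern.** The primary outcome is the one thing a protocol has to fix without ambiguity, and here two current sections fix it differently. A statistical analysis plan can supply a multiplicity method, but it cannot tell which of two conflicting protocol lists governs.

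Without a deciding outcome or time, the trial has no stated rule for success. The choice of headline result could be made after data are seen. The protocol leaves room for that: Section 8 plans analysis of accumulated data while recruitment continues (November 2026 to August 2027) and conference presentation in late 2027, with data collection continuing in early 2028. Section 3.7 states blinding for participants only.

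Separately, if the primary objective promises effects that no outcome measures, those aims cannot be answered whatever the data show.

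**Working it through.** **Step 1. The two lists side by side.**

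| Outcome | Synopsis | Section 3.8 |
|---|---|---|
| Fugl-Meyer | primary; no limb section or time | primary; upper extremity, two times |
| Brunnstrom, MAS | secondary | primary, two times |
| Neuroimaging | primary; CT/MRI, no index | primary; five MRI/DTI indices |
| EEG power and connectivity, rest and task | primary | primary |
| Complete blood count, CRP, IL-6, S100β, BDNF | primary | secondary |
| Muscle strength, comfort | secondary | absent |

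The lists agree on three families and conflict on the other clinical scales and on the blood markers. FMA-UE is the only clinical scale that is primary in both.

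**Step 2. Minimum number of primary tests.**

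- Section 3.8: 3 scales × 2 times + 5 imaging indices + 2 EEG states × 2 measures = 6 + 5 + 4 = 15.
- Synopsis: 1 Fugl-Meyer + at least 1 imaging + 4 EEG + 5 laboratory items = 11.

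Both are floors, since brain regions, frequency bands, channels and blood-count components are not fixed.

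**Step 3. False-positive risk if any one result suffices.** Assumptions, not stated in the protocol: two-sided 0.05 per test, and success on any single test. For k independent tests the risk is 1 − 0.95^k.

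- k = 15: 1 − 0.95^15 = 0.537.
- k = 11: 1 − 0.95^11 = 0.431.

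With equally correlated normal test statistics (400,000 simulated draws):

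| Common correlation | 15 tests | 11 tests |
|---|---|---|
| 0.3 | about 46% | about 37% |
| 0.5 | about 36% | about 30% |
| 0.7 | about 26% | not run |
| 0.8 | about 20% | about 18% |

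**Step 4. The opposite rule, all must succeed.** Type I error is then not inflated, but power falls. At an assumed effect of 0.8 SD on every outcome with 30 per group, single-test power is 0.861. For independent outcomes the joint power is 0.861^15 ≈ 0.11, or 0.861^11 ≈ 0.19. Correlation would raise both.

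**Step 5. What 30 per group can detect.** Section 3.2 gives the sample size of 60 with no endpoint, effect size, SD, alpha or power, so it cannot be reproduced and it points to no implicit primary outcome. Assuming 80% power, two-sided 0.05 and no dropout, one endpoint gives (1.960 + 0.842) × √(2/30) = 0.72 SD by the normal approximation, or 0.74 SD by the noncentral t. With Bonferroni over 11 or 15 tests (alpha 0.00455 or 0.00333) the noncentral t gives 0.98 or 1.01 SD.

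**Step 6. Objective against outcomes.** Of the four goals, only motor ability has a measure in either list. The scales named at screening (Section 3.5.4) are Fugl-Meyer, Brunnstrom and MAS. The latest follow-up named is 2 weeks, which cannot show long-term disability. Section 3.6 sets one intensity and one pulse sequence for everyone, so there is no contrast between parameter settings.

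**Step 7. CT.** The only CT described in Section 3.6 is one taken near stroke onset; the post-test is MRI. CT therefore has no post-treatment value to compare.

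**The case against.** The best defence has four parts.

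*The lists overlap, and multiplicity may be handled in an analysis plan not shown.* Both points are true. A reader might infer that the two lists are wholly different; the text does not support that, as Fugl-Meyer, neuroimaging and EEG are primary in both. But the conflict over Brunnstrom, MAS and the blood markers stands, and an analysis plan cannot settle which list governs.

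*The error rates depend on assumptions.* This stands. A reader might infer that the trial's type I error is 54%. The protocol gives no alpha and no any-one rule, the independent case is the upper of those computed, and scales repeated at two times are bound to be correlated. A reader might equally take the outcomes as co-primary in the strict sense, with all having to succeed; the protocol does not say that either. It simply holds multiple primary outcomes with no success rule.

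*MRI and EEG belong to the purpose of the study.* The objective does ask how the intervention works, using EEG and MRI. That is a fair reason to keep a mechanistic objective, but not to leave it mixed with the efficacy decision.

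*The CT entry may be synopsis shorthand.* This is plausible, since Section 3.8 limits imaging to functional MRI and diffusion indices. It is a minor part of the mismatch.

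**Conclusion.** The point stands and should be corrected before allocation starts. Three defects rest on the text alone: two current primary outcome lists that contradict each other in part, no deciding outcome or time within either list, and a primary objective that names cognition, long-term disability, quality of life and parameter optimisation without an outcome or a contrast to address them.

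The size of the multiplicity problem is conditional. Under the any-one rule at 0.05, the 15-test list carries a risk between about 26% (correlation 0.7) and 54% (independence), and still about 20% at correlation 0.8. These figures illustrate what the open choice could cost; they are not a property that the protocol fixes. Nor do the documents support calling the sample size of 60 wrong, because it is tied to no endpoint against which it could be checked.

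**What to change.** - **Outcomes.** Make the synopsis and Section 3.8 identical. Name FMA-UE at one stated time as the single primary outcome, tested at two-sided 0.05.
- **Schedule.** Section 3.6 describes a one-week protocol with an MRI post-test, and sets out neither a 2-week visit nor a post-treatment scale assessment. If the 2-week time is chosen, add that visit and its scale assessment there; if the immediate time is chosen, add its scale assessment.
- **Secondary outcomes.** List FMA-UE at the other time, Brunnstrom, MAS, muscle strength and comfort, in both places.
- **Mechanistic outcomes.** Label MRI, EEG and blood markers as mechanistic (secondary or exploratory), separate from the efficacy decision, with false-discovery control within each family. Drop CT from the synopsis outcome.
- **Objective.** In both the synopsis and Section 2.1, limit the primary objective to the effect of tFUS versus sham on FMA-UE. Keep the EEG/MRI mechanism question as a secondary objective. Remove the unmeasured aims and parameter optimisation. Adding cognition, disability and quality-of-life measures is an alternative to removing those aims, but it adds assessments, and a 2-week follow-up would still not show long-term disability.

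**Cost.** Imaging, EEG and laboratory results could no longer be claimed as confirmatory. The amendment needs prior Ethics Committee approval under Section 6.1. The version is dated April 27, 2026 and Section 8 plans allocation from June 2026. If that schedule holds, the change can precede any outcome data, although the interval is short.

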3.1 Study Design

This study is a randomized, controlled, single-center trial.

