3.2 Sample Size

Participants will be recruited from inpatients of the Department of Rehabilitation Medicine. Based on preliminary literature review and the current inpatient volume of our department, the provisional sample size is set at $n = 60$, with 30 participants allocated to each group.

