3.7 Control Group Intervention

The control group receives sham stimulation during the neuromodulation phase. All procedural steps are identical to those of the experimental group, including neuronavigation positioning, application of coupling gel, and all other preparatory procedures; however, ultrasound stimulation is not activated. Participants in the control group wear bone-conduction headphones to simulate and counteract acoustic confounding. Group allocation information is blinded to participants.

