November 2026 – August 2027: Continued case recruitment, statistical analysis of accumulated data, and objective evaluation of outcome measures across groups.

September 2027 – December 2027: Participation in provincial and national rehabilitation conferences, with preliminary findings presented for peer review and scholarly exchange.

January 2028 – February 2028: Continuation of clinical data collection, synthesis of completed research, comprehensive data analysis, and evaluation of study outcomes.

March 2028: Project completion, manuscript preparation, and publication.

9. Research Team

Name	Title / Specialty	Responsibilities
[name]	Chief Physician	Quality Control
[name]	Chief Physician	Data Analysis
[name]	Associate Chief Physician	Case Recruitment
[name]	Chief Physician	Data Analysis
[name]	Associate Chief Physician	Manuscript Preparation
[name]	Attending Physician	Case Recruitment
[name]	Attending Physician	Case Recruitment
[name]	Attending Physician	Case Recruitment
[name]	Attending Physician	Case Recruitment
[name]	Attending Physician	Rehabilitation Assessment
[name]	Senior Therapist	Rehabilitation Assessment

10. References

- [1] GBD 2021 Causes of Death Collaborators. Global burden of 288 causes of death and life expectancy decomposition in 204 countries and territories and 811 subnational locations, 1990–2021: a systematic analysis for the Global Burden of Disease Study 2021. *Lancet*. 2024;403(10440):2100.

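### Only participants are masked, while section 8 compares groups before data are complete, so the primary MRI and EEG values are open to arm-aware processing

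*Protocol*

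**What the plan says.** **Outcomes.** Section 3.8 places among the primary outcomes "neuroimaging data (analysis of ALFF, fALFF, ReHo, FC, and FA indices using functional MRI and diffusion tensor imaging" and "EEG measurements of resting-state and task-state spectral power and functional connectivity". The synopsis also lists neuroimaging and EEG as primary, although it names cranial CT/MRI there and not the individual indices.

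**Masking.** Section 3.1 describes the design in one sentence, "This study is a randomized, controlled, single-center trial", and names no level of blinding. Section 3.7 holds the only masking statement: "Group allocation information is blinded to participants". Nothing in the protocol extends this to those who process MRI or EEG files, decide exclusions or analyse the data. No coding of files is described.

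**Timing.** Section 8 plans, for November 2026 to August 2027, "Continued case recruitment, statistical analysis of accumulated data, and objective evaluation of outcome measures across groups". For September to December 2027 it plans conference participation "with preliminary findings presented for peer review and scholarly exchange". For January to February 2028 it plans "Continuation of clinical data collection, synthesis of completed research, comprehensive data analysis, and evaluation of study outcomes". No data lock or firewall is described between these steps.

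**The concern.** ALFF, fALFF, ReHo, functional connectivity, FA and EEG spectral measures are not direct readings. Someone decides which epochs and channels to reject, which scans to drop for motion, how to mask the lesion, and which seed, band or threshold to use. If that person knows the arm, or has seen how the groups are diverging, each choice can lean towards the hoped-for result without any intent to mislead.

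The primary objective relies on EEG and MRI to show network remodeling, so these outcomes are meant to be the trial's objective evidence. The issue is how the values are produced. It is separate from bedside rating and from repeated testing: adjusting the significance level for interim looks would leave arm-aware processing untouched.

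**Working it through.** **Step 1: passages side by side.**

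| Question | Protocol | Answer |
|---|---|---|
| Are MRI and EEG primary? | Synopsis; 3.8 | Yes, in both lists |
| Who is masked? | 3.7 | Participants |
| Are MRI/EEG processors masked, or files coded? | No statement | Not provided for |
| Are groups compared before recruitment ends? | Section 8, Nov 2026 to Aug 2027 | Yes |
| Are findings shown before data collection ends? | Section 8, Sep to Dec 2027, then Jan to Feb 2028 | Yes |

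Together these allow the arm and the emerging difference to be known while later files are still to be processed.

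**Step 2: choosing among settings (illustration).** The protocol gives no figure to reproduce here, and the inputs are assumptions: no true effect; k defensible processing settings; their test statistics standard normal with common correlation r; the most favourable one kept; success in favour of treatment at z > 1.96 (nominal 2.5%, from an assumed two-sided 5%). With φ and Φ the normal density and distribution function:

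P(max Z > 1.96) = 1 − ∫ φ(u) · Φ((1.96 − √r·u)/√(1−r))^k du

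| k | r = 0.5 | r = 0.7 | r = 0.9 |
|---|---|---|---|
| 3 | 6.3% | 5.5% | 4.2% |
| 5 | 9.2% | 7.4% | 5.1% |
| 10 | 14.4% | 10.7% | 6.4% |

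The range is about 4% to 14% against 2.5%. With 5 settings correlated 0.7 it is about 7%, roughly three times nominal (7.4/2.5 ≈ 3.0).

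**Step 3: excluding files (worst case).** Section 3.2 plans 60 participants, "with 30 participants allocated to each group". The simulation used 40,000 null trials with 30 per arm, a standard normal outcome and an independent-samples t-test (the synopsis test for normally distributed data). It dropped the least favourable files in each arm and counted p < 0.05 in favour of treatment.

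| Files dropped per arm | Chosen knowing arm and value | Dropped at random |
|---|---|---|
| 1 | 8.7% | 2.3% |
| 2 | 20.5% | 2.3% |
| 3 | 35.8% | 2.4% |

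Three files are 10% of an arm (3/30). Perfectly adverse selection is an extreme, not a forecast. It shows only that, at this size, a few exclusions can decide a result.

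**The case against.** **Much of this could sit in the SAP.** Artefact rules, motion limits, and choice of band, seed and threshold are commonly left to an SAP or imaging manual, and that document is not shown. This stands: their absence from the protocol is not the finding. Who is masked is protocol content, however. The protocol addresses it, names participants only, and then schedules group comparisons before data are complete.

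**Section 8 is general.** It does not name MRI or EEG, or say that processing settings are revisited. That is so, and tuning is therefore a possibility and not a plan. But both are primary outcomes, and nothing excludes them from the evaluation across groups.

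**The illustration may overstate the effect.** It assumes selection on the complete data. Settings chosen on early files and then kept for later ones would inflate the error less.

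**Stronger readings that the documents do not support.**
- A reader might put the error rate at about 8% to 29% against 5%. That is the chance that the most extreme of the settings is significant in either direction, so it counts results against treatment. It does not describe keeping the favourable result.
- A reader might infer that the damage is permanent. Recorded MRI and EEG files can be recoded and reprocessed by masked staff if they are kept, and nothing says they are discarded.
- A reader might infer from the section 9 team table, which names no stimulator operator, that an operator also analyses data. The table does not show this. It also lists quality control and manuscript roles, and section 3.5.1 plans to recruit and train further personnel.
- Calling these outcomes co-primary goes too far: the protocol calls them primary and gives no rule for combining them.

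**Coding is not a complete remedy.** Section 3.6 has EEG recorded during stimulation, at least in sessions 2 and 5, and the sham is not activated. If the active device leaves a visible trace, which is an assumption, a code will not hide the arm in those recordings. This stands and limits the fix.

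**Conclusion.** The concern holds as one of exposure. The protocol masks participants only, makes neuroimaging and EEG primary, and schedules between-group evaluation and presentation before data collection ends. Followed as written, it lets the people who process these files and decide exclusions know the arm and the emerging difference. It does not show that they will, or that any result would be biased.

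The size is illustrative: about 4% to 14% false positives in favour of treatment instead of 2.5%, per outcome, and about 7% for 5 settings correlated 0.7. This rests on no true effect, equal correlation, selection of the most favourable setting on the full data, and an assumed two-sided 5% level. The change should be made, because it protects primary outcomes at little cost. Section 8 starts randomization in June 2026, after the version date of April 27, 2026, so on that schedule it could be in place from the first participant.

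**What to change.** **Sections 3.7 and 3.8.** State that:
- every MRI and EEG file carries an arm-neutral code;
- files are processed, and exclusions decided, without access to allocation, by existing staff who do not operate the stimulator;
- indices and exclusions are locked before the allocation key is merged.

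**Section 8.** Amend the timeline so that by-arm MRI and EEG results are neither evaluated nor presented before that lock.

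**EEG during stimulation.** Apply artefact rules set in advance, and rely mainly on the recordings made before and after stimulation, where a device trace should not reveal the arm.

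**Cost.** Protocol wording, plus file coding by whoever holds the allocation list. No additional patients or scans are needed, and no additional staff provided that someone already on the team can process files without operating the stimulator. The downside is delay: by-arm imaging and EEG results, including any conference presentation of them, wait for the lock.
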